8.4 EXPEDITED REPORTING OF ADVERSE EVENTS

BI is responsible to fulfil their legal and regulatory reporting obligation in accordance with regulatory requirements.

8.5 STATEMENT OF CONFIDENTIALITY AND PARTICIPANT PRIVACY

Data protection and data security measures are implemented for the collection, storage and processing of participant data in accordance with the principles 7 and 12 of the WHO GCP handbook.

Individual participant data obtained as a result of this study is considered confidential and disclosure to third parties is prohibited with the following exceptions:

Personalised treatment data may be given to the participant's personal physician or to other appropriate medical personnel responsible for the participant's welfare. Data generated at the site as a result of the study need to be available for inspection on request by the sponsor's representatives, by the IRB / IEC and the regulatory authorities.

8.6 STUDY MILESTONES

The **start of the study** is defined as the date when the first participant in the whole study signs e-informed consent.

The end of the study is defined as the date of the last visit of the last participant in the whole study ("Last Participant Completed"). Early termination of the study is defined as the premature termination of the study due to any reason before the end of the study as specified in this protocol.

Temporary halt of the study is defined as any unplanned interruption of the study by the sponsor with the intention to resume it.

Suspension of the study is defined as an interruption of the study based on a Health Authority (HA) request.

8.7 ADMINISTRATIVE STRUCTURE OF THE STUDY

The study is sponsored by Boehringer Ingelheim (BI).

Relevant documentation on the participating (Principal) Investigators (e.g. their curricula vitae) will be filed in the ISF.

BI has appointed a Study Team Lead, responsible for coordinating all required activities, in order to

- manage the study in accordance with applicable regulations and internal SOPs,
- direct the study team in the preparation, conduct, and reporting of the study
- ensure appropriate training and information of the investigator.

16 Sep 2021

Page 53 of 93

Proprietary confidential information © 2021 Boehringer Ingelheim International GmbH or one or more of its affiliated companies

The organization of the study in the participating countries will be performed by a Contract Research Organization (CRO) with which the responsibilities and tasks will have been agreed and a written contract filed before initiation of the clinical study.

The web-based platforms used to capture data collected in the study and for TARA will be developed by a digital technology provider with which the responsibilities and tasks will have been agreed and a written contract filed before initiation of the clinical study.

Data Management and Statistical Evaluation will be done in collaboration with an external consultant

Tasks and functions assigned in order to organise, manage, and evaluate the study are defined according to BI SOPs. A list of responsible persons and relevant local information can be found in the ISF.

16 Sep 2021

Clinical Study Protocol Outline Page 54 of 93

Proprietary confidential information © 2021 Boehringer Ingelheim International GmbH or one or more of its affiliated companies

10. APPENDICES

10.1 DETAILS OF EX-TARA ASSESSMENT TOOLS

10.1.1 Baseline, Interim and Follow-up Survey Assessments

The baseline survey will be provided to participants before they have access to the TARA program. See flow chart for a complete list of survey timepoints.

Survey 1 will be administered at the end of the run-in period and will contain the following elements:

- Chronic Respiratory Questionnaire Self Administered Individualized (CRQ-SAI)
- Clinical Visit PROactive Physical Activity in COPD Instrument (C-PPAC)
- A Knowledge assessment for COPD self-management
- Treatment Self-Regulation Questionnaire (TSRQ)
- Perceived Competence Scale (PCS)
- Health Care Climate Questionnaire (HCCQ)
- Medication adherence questions
- COPD Assessment Test (CAT)
- Hospital Anxiety and Depression Scale (HADS)
- Questions assessing barriers to medication adherence

Interim surveys during the TARA usage period include the following.

Surveys 2, 3 and 4 will be administered at 2, 4 and 8 weeks from start of study respectively and will contain the following elements:

- Chronic Respiratory Questionnaire Self Administered Individualized (CRQ-SAI)
- Readiness to change
- Perceived Competence Scale (PCS)

Survey 5 will be the 12-week survey and will contain the following elements:

- Chronic Respiratory Questionnaire Self Administered Individualized (CRQ-SAI)
- Clinical Visit PROactive Physical Activity in COPD Instrument (C-PPAC)
- Readiness to change
- A Knowledge assessment for COPD self-management
- Treatment Self-Regulation Questionnaire (TSRQ)
- Perceived Competence Scale (PCS)
- Virtual Care Climate Questionnaire (VCCQ)
- Questions measuring medication adherence, PLB and pacing
- COPD Assessment Test (CAT)
- Hospital Anxiety and Depression Scale (HADS)
- Questions assessing barriers to medication adherence
- Healthcare resource utilization

[figure not shown]
Survey 6 will be the final survey administered after the follow-up clinic visit and will contain the following elements:

• System Usability Scale (SUS) https://measuringu.com/sus/

16 Sep 2021

Page 61 of 93

- 'Perceived value and satisfaction of TARA' Questions
 - These questions will explore participants satisfaction and willingness to recommend TARA (from Net Promoter Score (NPS) Survey)

16 Sep 2021

Clinical Study Protocol Outline Page 62 of 93

Proprietary confidential information © 2021 Boehringer Ingelheim International GmbH or one or more of its affiliated companies

[figure not shown]

10.3 QUALITATIVE INTERVIEW SAFETY PROTOCOL

In all contacts between interviewers and study participants, the content of the discussion will be monitored for Adverse Events as detailed in Section 5.3.6.

During a qualitative interview, the participant may disclose information about unmet needs, personal risks, changes they have made (or intend to make) to medication taking behaviours or health concerns, and the interviewer has a responsibility to recommend the participant consults their personal physician or other relevant agencies.

If the participant discloses the following kind of information during the interview, the interviewer has a responsibility to refer the participant to an appropriate healthcare provider or agency or support group as follows:

- Participant discloses information about possible medical condition, side-effect, change to medication taking that is not in line with their physician's instructions, or symptom: interviewer to recommend participant to consult their personal physician or emergency service
- 2. Participant discloses information about physical or mental harm or abuse, or the risk of harm or abuse, to themselves or others: interviewer to recommend participant to contact social services or police.

Clinical Study Protocol Outline

16 Sep 2021

Page 91 of 93

Proprietary confidential information © 2021 Boehringer Ingelheim International GmbH or one or more of its affiliated companies

11. DESCRIPTION OF GLOBAL AMENDMENT(S)

11.1 AMENDMENT 1

Date of amendment	16 Sep 2021	
EudraCT number	NA	
EU number		
BI Trial number	352-2154	
BI Investigational Medicinal	TARA DBCI prototype (version 3)	
Product(s)		
Title of protocol	Proof of concept (proof of intervention	
	principles) study assessing effects of Technology-	
	Assisted Respiratory Adherence prototype	
	version 3 (a Digital Behaviour Change	
	Intervention, DBCI) on proximal clinical	
	outcomes and mediators (psychological	
	mediators, self-management behaviours) in	
	individuals with COPD (IwCOPD)	
Global Amendment due to urgent sa	afety reasons	
Global Amendment		X
	L my d	
Section to be changed	Title page	
Description of change	Allocation of new CTL	
Rationale for change	Change in CTL	
Section to be changed	Sections 2.3, 5.1.3.1, 10.1.1, 10.2.5.	
Description of change		
Section to be changed	Synopsis, Section 3.3.3	"
Description of change	Exclusion criterion 1 – updated from	
	with asthma" to "Patients with asthma as	
	concurrent baseline condition at the time of	
	screening"	
Rationale for change	Clarification to all enrolment of patients with a	
	historical diagnosis of asthma	
Section to be changed	Synopsis, Section 3.3.3	
Description of change	Exclusion criterion 2 - updated to include a	
	timeframe for contacts with an infected person	
	prior to the completion of the eligibility	
	questionnaire.	

16 Sep 2021

Page 92 of 93

Rationale for change	Updated to allow the enrolment of patients who have been in contact with persons infected with SARS COV-19, but are not infected themselves	
Section to be changed	Section 5.3.7	
Description of change	All AEs and SAEs are to be reported to BI GPV regardless of causal relationship to Spiriva Respimat or Stiolto Respimat	
Rationale for change	Clarification of AE reporting requirements to ensure all identified events will be evaluated and reported accordingly.	
Section to be changed	Synopsis, Sections 3.1, 7.2.7	
Description of change	Removal of interim analysis	
Rationale for change	Based on the observed TARA use by the first enrolled patients of cohort 1, an interim analysis between cohort 1 and cohort 2 is no longer expected to provide meaningful results.	
Section to be changed	Section 7.2.1	
Description of change	Clarification that cohorts 1 and 2 will be analysed separately and definition of analysis data set	
Rationale for change	Further clarification on planned data analysis	
Section to be changed	Section 7.2.5.	

## 2. LIST OF ABBREVIATIONS

Term	Definition / description
C-PPAC	Clinical Visits PROactive Physical Activity in COPD
CRQ-SAI	Chronic Respiratory Questionnaire – Self Administered Individualized
CSP	Clinical Study Protocol
IwCOPD	Individuals with chronic obstructive pulmonary disease
MCID	Minimal Clinically Important Difference
SSAP	Study Statistical Analysis Plan

## 3. INTRODUCTION

As per ICH E9 ( $\underline{1}$ ), the purpose of this document is to provide a more technical and detailed elaboration of the principal features of the analysis described in the protocol, and to include detailed procedures for executing the statistical analysis of the primary and secondary variables and other data.

This SSAP assumes familiarity with the Clinical Study Protocol (CSP), including Protocol Amendments. In particular, the SSAP is based on the planned analysis specification as written in CSP Section 7 "Statistical Methods and Determination of Sample Size". Therefore, SSAP readers may consult the CSP for more background information on the study, e.g., on study objectives, study design and population, treatments, definition of measurements and variables, planning of sample size.

SAS® Version 9.4 will be used for all analyses.

#### 4. CHANGES IN THE PLANNED ANALYSIS OF THE STUDY

As a result of the limited sample size (5 instead of the planned 50 individuals with chronic obstructive pulmonary disease (IwCOPD), the pre-planned analyses for this study will not be conducted. Instead, listings of participants' data will be generated for inclusion in an abbreviated study report. The primary and secondary assessments will be listed for each participant, and from the further assessments, only the engagement with TARA will be listed. No subgroup analyses will be performed.

## 5. ASSESSMENTS

#### 5.1 PRIMARY ASSESSMENT

Primary assessments are listed below and in CSP Section 2.1.2.

- Change from baseline in the Chronic Respiratory Self Administered Individualized (CRQ-SAI) dyspnea domain score at 12 weeks.
- Increase from baseline in the CRQ-SAI dyspnea domain score at 12 weeks of at least 0.5, the minimal clinically important difference (MCID).

#### 5.2 SECONDARY ASSESSMENTS

Secondary assessments are listed below and in CSP Section 2.2.2.

# 5.2.1 Activity Tracker ( device)

- Change from baseline in average number of steps measured by the activity tracker at Week 12.
- Change from baseline in average cadence (steps/min) measured by the activity tracker at Week 12.
- 5.2.2 Clinical Visit PROactive Physical Activity in COPD instrument (C-PPAC)
  - Change from baseline in the difficulty domain of the Clinical Visits PROactive Physical Activity in COPD instrument (C-PPAC) at Week 12.

SSAP for BI Study No: 0352-2154

Proprietary confidential information © 2022 Boehringer Ingelheim International GmbH or one or more of its affiliated companies

## 5.4 OTHER VARIABLE(S)

# 5.4.1 Demographics and baseline characteristics

Baseline is defined in Section 6.7.

Demographics and other baseline characteristics will include the following.

- Gender
- Race
- Ethnicity
- Age [years]
- English fluency
- State
- Time zone
- Smoking status
- Background Treatment

## 6. GENERAL ANALYSIS DEFINITIONS

#### 6.1 TREATMENT(S)

Treatment specification is not applicable as there are no pharmacological treatments assigned nor administered as part of the study. Analyses will be performed separately by cohort, as different versions of TARA were used.

The following study periods will be defined with respect to safety analyses:

• Post-Informed-Consent: after informed consent

#### 6.2 IMPORTANT PROTOCOL DEVIATIONS

The following table defines the different categories of important protocol deviations (iPDs) to be considered. Patients with iPDs will be excluded from analyses specified in Table 6.2: 1. In addition, the frequency of participants with iPDs will be summarized descriptively.

Table 6.2: 1 Important protocol deviations

Category /		Description	Requirements	Excluded from which
Code				analysis set
Α		Entrance criteria not met		
	A1	Inclusion criteria not met	Inclusion criteria not met as specified in the protocol.	None
	A2	Exclusion criteria not met	Exclusion criteria not met as specified in the protocol.	None
В		Informed consent		
	B1	Informed consent not available/not done	Informed consent missing	All
	B2	Informed re-consent not available/not done	Informed re-consent missing	All

#### 6.3 SUBJECT SETS ANALYSED

The following subject set will be used in the analysis:

Entered set (ES):
This subject set includes all enrolled subjects with informed consent who completed the baseline
Survey (Survey 1).

The ES will be used for all assessments.

#### 6.5 POOLING OF CENTRES

This section is not applicable because center is not included in the analysis.

#### 6.6 HANDLING OF MISSING DATA AND OUTLIERS

In general, the efficacy analyses as well as safety analyses will be evaluated by observed case analysis, i.e., using only available data without imputation.

#### 6.6.1 Primary Assessment

For the primary assessment, imputation of missing values will not be performed, as per the CRQ-SAI manual.

## 6.6.2 Secondary and Further Assessments

For secondary and further assessments, imputation of missing values will not be performed.

### 6.6.3 Safety assessments

Missing or incomplete adverse event (AE) dates are imputed according to BI standards (refer to 2 and 3).

## 6.7 BASELINE, TIME WINDOWS AND CALCULATED VISITS

Generally, last assessment before day of TARA initiation (included) will be used as baseline. Time windows will not be used. Baseline will be defined as administration of Survey 1, and Week 12 as administration of Survey 5.

The following measurements will be included for analysis and in the calculation of average of the activity tracker tool scores.

- Survey 1: Baseline measure = 14 days before and up to (including) baseline
- Survey 5: Week 12 measure = 14 days before and up to (including) Week 12

#### 7. PLANNED ANALYSIS

All the assessments (primary, secondary and further), as well as the demographics and baseline characteristics, will be presented as listings for participants, on the ES.

Customized listings will be developed for presenting the participant data, including participant identifier, cohort and specific measurement(s).

#### 7.1 DEMOGRAPHIC AND OTHER BASELINE CHARACTERISTICS

Only listings are planned for this section of the report.

#### 7.2 CONCOMITANT DISEASES AND MEDICATION

Not applicable due to limited data collected.

#### 7.3 TREATMENT COMPLIANCE

This section is not applicable as there were no treatments administered nor assigned in this study. Instead of compliance, the engagement with TARA will be analyzed.

### 7.4 PRIMARY ASSESSMENTS

The primary assessments will be conducted on the ES.

For each participant, the CRQ-SAI dyspnea domain score will be calculated as the mean of numerical answers to the questions 1, 2, 3, 4, 5, excluding those questions not answered. The range for each numerical answer is 1-7 (with 1 being the worst and 7 the best). The primary endpoint is increase in dyspnea domain score from baseline to Week 12 of at least 0.5 (MCID), so Dyspnea-score-Week12 – Dyspnea-score-baseline >= 0.5 will be marked as Yes. The change from baseline in CRQ-SAI dyspnea domain score at Week 12 will also be reported. More details about the CRQ-SAI dyspnea domain score calculation appear in Section 10.1.

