5. FURTHER DETAILS REGARDING ASSESSMENTS

5.1 ASSESSMENT OF EFFICACY

5.1.1 Primary Assessment

Chronic Respiratory Questionnaire – Self Administered Individualized (CRQ-SAI)

The CRQ-SAI, a derivate of the original CRQ tool, is used to assess the patients' perception of their COPD and measures the impact of COPD on their life. The CRQ-SAI has 20 items over 4 domains: dyspnea, fatigue, emotional function and mastery. For dyspnea, participants are asked to select 5 activities associated with breathlessness (from a list of 26 or custom response), that they have performed in the past two weeks and that are most important to them and indicate how much breathlessness they have experienced while performing each.

The CRQ-SAI should be completed by the participants at the time points outlined in the flow chart. Details of the CRQ-SAI are provided in Appendix 10.2.1.

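### Does SAP 7.4 need an item-matching rule so that a CRQ-SAI item answered at only one survey cannot flip the listed 0.5-point flag?

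*SAP*

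**What the plan says.** SAP 7.4 defines the score at each visit as the "mean of numerical answers to the questions 1, 2, 3, 4, 5, excluding those questions not answered". Each answer runs from 1 (worst) to 7 (best). The responder rule is "Dyspnea-score-Week12 – Dyspnea-score-baseline >= 0.5 will be marked as Yes", and the change itself is also reported. The section closes its scoring description with a pointer: "More details about the CRQ-SAI dyspnea domain score calculation appear in Section 10.1".

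SAP 6.6.1 adds that "imputation of missing values will not be performed, as per the CRQ-SAI manual". Protocol 5.1.1 explains that the dyspnea items are individualized: participants choose five activities "that they have performed in the past two weeks and that are most important to them".

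Because 5 rather than 50 participants were available, SAP 4 replaces the planned analyses with listings for an abbreviated report: "The primary and secondary assessments will be listed for each participant". SAP 7 describes these listings in open terms: they include an identifier, the cohort and the measurements concerned.

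**The concern.** An available-item mean at one visit is subtracted from an available-item mean at another. If the two means rest on different items, the difference mixes a change in breathlessness with a change in which activities were rated. The change and the flag are the two primary assessments, and with listings only, each flag is read on its own, with no group estimate to dilute an error.

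The instrument makes the worry plausible. An activity given up because of breathlessness might be left blank at Survey 5, and it would tend to be a low-scoring one. Dropping it raises the Week 12 mean. What is at stake is a false Yes or a false No for a single listed participant.

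**Working it through.** **Inputs.** From SAP 7.4: items scored 1 to 7, five items, mean of those answered, threshold 0.5. From SAP 4: 5 participants. The documents give no rate of skipped items and no between-item spread, so those are assumptions below. The plan states no figure of its own to reproduce on this point.

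**One item skipped at Week 12, no true change.** Let M be the five-item mean and x the skipped item.

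- Listed change = (5M − x)/4 − M = (M − x)/4.
- A false Yes needs (M − x)/4 ≥ 0.5, so the skipped item must lie at least 2 points below the five-item mean. Equivalently, it lies at least 2.5 points below the mean of the other four.
- If all items lie within 3-5 (or within 2-4), the largest artefact is (5 − 3)/5 = 0.4, so a false Yes cannot occur.
- The five deviations M − x sum to zero, so a randomly skipped item causes no bias on average.

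**Worked cases.**

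- False Yes: 4,4,4,4,1 then 4,4,4,4,blank. 17/5 = 3.4; 16/4 = 4.0; change +0.6.
- False No: 2,3,3,4,6 then 3,4,4,5,blank. 18/5 = 3.6; 16/4 = 4.0; change +0.4. The four common items went from 12/4 = 3.0 to 4.0, a rise of 1.0.
- No skip and the same activities: the SAP change and the common-item change are identical.

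**Would a common-item flag be better?** Two illustrative simulations compare each flag with the flag from all five answers, always given one random Week 12 skip.

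In the first, the person mean is N(3.5, 0.9), item SD is 0.75/1.0/1.25, and zero to four items rise by exactly 1 point:

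| Full five-item change | SAP 7.4 flag wrong (%) | Common-item flag wrong (%) |
|---|---|---|
| 0 | 0.3 / 1.6 / 3.8 | 0 |
| 0.2 | 8 / 13 / 17 | 0 |
| 0.4 | 38 / 39 / 40 | 60 |
| 0.6 | 29 / 32 / 34 | 0 |
| 0.8 | 5 / 9 / 13 | 0 |

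The common-item column is exact. At 0.4, two items rise. If the skipped item is one of the three that did not rise (3/5 = 60%), the common change is 2/4 = 0.5, a false Yes; otherwise it is 1/4 = 0.25. At 0.6, three items rise and the common change is 2/4 or 3/4, both Yes, which is correct.

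The second simulation adds item-level noise at Week 12 (SD 0.8), with item SD 0.7 to 1.5 and mean change 0 to 0.75. The SAP flag disagrees with the complete flag in 9.8% to 23.8% of cases and the common-item flag in 10.9% to 16.8%. With narrow item spread and no mean change, the SAP score does slightly better (9.8% against 11.1% at item SD 0.7). With wide spread the common-item score does better (16.8% against 23.8% at item SD 1.5 and mean change 0.5).

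**The case for a change.** The best case for a change is this. The flag is a primary assessment, read one person at a time. Protocol 7.2.1 itself insists that an apparent gain in breathlessness must not come from reduced activity, and the analysis planned to check that was dropped with the rest. SAP 7.5 sets a completeness rule for the step count (at least 4 valid days of 14), while 7.4 shows none for the primary score. If the single worst item is the one skipped, with no true change, the false-Yes rate under the first set of assumptions is 2/8/18% rather than 0.3/1.6/3.8%. Listing the number of items answered would cost almost nothing.

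Part of this stands. Section 7.4 on its own does not state a matching or minimum-item rule, and one skipped item can move a flag either way.

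The rest does not carry. Section 10.1 of the SAP is devoted to CRQ-SAI dyspnea scoring and is where such a rule would sit; its absence from the copy reviewed is not an omission in the plan. Protocol 5.1.1 describes how activities are chosen but does not say they are chosen afresh at Survey 5. The description of the listings neither promises nor excludes item answers or counts, so it cannot be said that a skip would be hidden. Because the wording is open, whoever builds the listing can show them without altering the SAP.

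**Conclusion.** The arithmetic is right but it does not call for a change. It describes what the formula in 7.4 could do to a participant who answered an item at only one survey; it does not show that the full scoring rule permits this or that it happened.

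The size is limited. The effect is nil when all five items for the same activities are answered at both visits. It can touch at most the 5 listed participants, and no test, percentage or decision rule uses the flag. With a random skip and no true change, the false-Yes rate is 0.3% to 3.8% under the assumed spreads. The rates of 29% to 40% arise only at full changes of 0.4 and 0.6, the steps on either side of the threshold, where the flag is easily tipped by losing one answer in five. The change is listed next to the flag, so a reader can see how near the cut it lies.

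The natural remedy, a common-item flag, is a trade-off. The documents tie the 0.5 MCID to the domain score as the SAP defines it and do not show that it applies to a subset of items. The common-item flag also does worse than the SAP's score in some plausible settings. What remains is scoring and display detail that an analyst working from Section 10.1 settles in the ordinary course.

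This rests on Section 10.1 not contradicting 7.4, and on simulated spreads and skips that are assumptions rather than trial data.
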